15.8.3. Procedures for Suspension or Termination

Medtronic-Initiated

- For deciding to suspend or terminate clinical trials, sponsor shall notify the management department of medical device clinical trials of all clinical trial institutions within 5 days, and state the rationale in written form.
- Management department of medical device clinical trials in clinical trial institutions shall timely notify corresponding investigators and Ethics Committee.
- The suspended clinical trials shall not be recommenced without the approval of Ethics Committee.
- Upon the completion of clinical trials, sponsor shall notify local food and drug regulatory authority of the province, autonomous region and municipality directly under the central government where he locates in written form.
- Upon receipt of notification of suspending or terminating clinical trials from sponsor, investigators shall timely notify subjects and ensure that subjects receive appropriate treatment and follow-up.
- In the case of a study suspension, subject enrollment must stop until the suspension is lifted by Medtronic with the approval of Ethics Committee.
- In the case of a study suspension, enrolled subjects should continue to be followed out of consideration of their safety, rights and welfare.

Clinical Trial Institution and Investigator-Initiated

- If it is required to suspend or terminate the trial as the clinical trial institution and investigators found that the risk outweighs the possible benefits or results have been obtained that suffice the judgment of the safety and effectiveness of medical device, the investigators shall inform the subjects, and make sure appropriate treatment and follow-up visits for the subjects, and meanwhile report as required with detailed written explanation for the suspension and termination.

- Clinical Trial Institution and Investigator shall report to the food and drug regulatory authorities of the provinces, autonomous regions and municipalities directly under the central government if necessary.
- In the case of a study suspension, subjects enrolled should continue to be followed out of consideration of their safety, rights and welfare.

EC/IRB-Initiated

- The investigator will inform Medtronic and provide a detailed written explanation of the termination or suspension within 5 business days
- Subject enrollment must stop until the suspension is lifted
- Subjects already enrolled should continue to be followed in accordance with Ethics
- Committee policy or its determination that an overriding safety concern or ethical issue is involved
- The investigator will inform his/her institution (where required per local requirements)
- Upon receipt of notification of suspending or terminating clinical trials from Ethics Committee, investigators shall timely notify subjects and ensure that subjects receive appropriate treatment and follow-up.

16. Appendixes

Appendix A: Informed Consent Form

The ICF template will be provided under a separate cover.

Xpede Clinical Investigation Plan

Version 3 17 Sep 2018

Page 78 of 78

Medtronic

Version History

Version	Summary of Changes	Author(s)/Title
1.0	
• New Document	[name], Clinical Research Sr. Manager [name], EMEA RCC Principal Proj and Clinical Research Spec
2.0	
• Updated indication for Use according to M708348B093E Rev C• Correction of minor typos	[name], EMEA RCC Principal Proj and Clinical Research Spec
3.0	
• Update inclusion criteria: age range between 18-80 years• Specification that the efficacy will be evaluated by a blinded investigator• Definition of a central image reading CoreLab• Removal of the CEC as not required by local regulation	[name], EMEA S&SS Principal Proj and Clinical Research Spec

Medtronic Confidential

This document is electronically controlled

056-F275, v3.0 Clinical Investigation Plan Template

Version	Summary of Changes	Author(s)/Title
1.0	
First Release	[name]

2. List of Abbreviations and Definitions of Terms

Abbreviation	Definition
AE	Adverse Event
BKP	KyphoPlasty Balloon
CEC	Clinical Events Committee
FAS	Full Analysis Set
ICH	International Conference on Harmonization
ITT	Intention To Treat
NRS	Numeric Rating Scale
ODI	Oswestry Disability Index
OVCFs	Osteoporotic Vertebral Compression Fractures
PPS	Per Protocol Set
PMM	PolyMethylMetacrylate
SF36	36-Item Short Form Health Survey
VP	VertebroPlasty

3. Introduction

Osteoporotic vertebral compression fractures (OVCFs) have gradually evolved into a serious health care problem globally. In order to reduce the morbidity of OVCF patients and improve their life quality, two minimally invasive surgery procedures, vertebroplasty (VP) and balloon kyphoplasty (BKP), have been developed. Both VP and BKP require the injection of bone cement into the vertebrae of patients to stabilize fractured vertebra. As such, bone cement as the filling material plays an essential role in the effectiveness of these treatments. The study will randomize subjects into two arms the Xpede and the Mendec as comparative products. The Mendec Bone Cement has been launched on China Market and has very similar composition material with the Kyphon®Xpede and they are both polymethylmetacrylate (PMM).™Bone Cement.

Due to these reasons the design of this study is a non-inferiority based on the margin δ as the maximum acceptable extent of clinical non-inferiority of Kyphon®Xpede™Bone Cement.

This SAP is based on Protocol Version 3, 17 Sep 2018 titled, "Xpede study". The SAP has been prepared in agreement with Medtronic internal procedures and using the CONSORT Statement¹ and International Conference on Harmonization (ICH) guidelines E3, E6 and E9 as guidelines.

Xpede Clinical Study

Statistical Analysis Plan

Version 1.0

Page 5 of 19

Medtronic

4. Study Objectives

4.1. Primary Objective and Endpoint

The primary objective of this study is composed by two primary endpoints aimed to demonstrate that Kyphon®Xpede™Bone Cement is effective by showing that:

- the mean change of Numeric Rating Sore (NRS) score from baseline at 6 months post operation in the subjects treated with Kyphon®Xpede™Bone Cement is non-inferior to that in the subjects treated with Mendec Spine Bone Cement;
- the mean change of Index Vertebral Body Angles from baseline at 6 months in the subjects treated with Kyphon®Xpede™Bone Cement is non-inferior to that in the subjects treated with Mendec Spine Bone Cement.

4.2. Secondary Objectives and Endpoints

The secondary endpoints include:

- Change of NRS score from baseline at 1 day and 3-month visit
- Change of ODI from baseline at 1 day, 3-month visit and 6-month visit
- Change of SF-36 from baseline at 1 day, 3-month visit and 6-month visit
- Change of Vertebral body height restoration at 1 day and 3-month visit and 6-month visit
- Change of Vertebral body Angles from baseline at 1 day, 3-month visit and 6-month visit
- Adverse events through 6-month visit. In particular, the following events will be reported:
 - Bone Cement Implantation Syndrome;
 - Bone Cement leakage;
 - Vertebral body compression fracture;
 - Adjacent vertebral body fracture;

5. Investigation Plan

The Xpede Study is a prospective, 1: 1 randomized, single blinded, multi-center human clinical trial designed to confirm the safety and efficacy profile of the Kyphon®Xpede™Bone Cement for regulatory approval in China. This study will enroll up to 180 subjects in order to demonstrate that the Kyphon®Xpede™ Bone Cement is non-inferior to the Mendec Bone Cement by more than a small pre-specified amount in terms of the primary endpoint. This amount is defined as the noninferiority margin (see section 13 from Protocol for details). Subjects will be randomly assigned with a 1:1 ratio to the Kyphon®Xpede™ Bone Cement arm or to the Mendec Bone Cement arm and then followed for a duration of 6 months in all sites. All study sites will be in China. Total duration of the study is anticipated to be approximately 12 months (6 months of enrollments and 6 months follow-up after study procedure).

Patients will be randomized 1:1 to either Xpede™ Bone Cement or Mendec bone cement. The sequence of treatments will be randomly permuted in blocks of 2 or 4 patients per block. The

Xpede Clinical Study

Statistical Analysis Plan

Version 1.0

Page 6 of 19

Medtronic

blocked randomization will be centralized and schedules will be created by the study statistician using statistical software. To minimize the selection bias, the randomization procedure for this study will use the site (3 sites), the number of vertebral to be treated (1,2 or 3) and the type of procedure (2 procedure: VP and BKP) as stratification factors, so that there will be a separate permuted block randomization list for each stratum (18). This guarantees treatment balance within strata.

[figure not shown]

Figure 1: Study Flowchart

6. Determination of Sample Size

Since the primary endpoint is composed of two efficacy endpoints, the sample was determined by the primary objective that requires the larger sample size. For the determination of the sample size

Xpede Clinical Study

Statistical Analysis Plan

Version 1.0

Page 7 of 19

Medtronic

for both endpoints the required power was 0.80, type I error 0.025. The sample size calculations were performed using SAS software (SAS Institute Inc., Cary, NC, USA). If we use $3 * 3 * 2$ strata the final sample size should be divisible by 18. More detail in section 13.1.2 of the protocol.

6.1. Primary Endpoint on NRS

The following assumptions were used for the determination of the sample size for NRS non-inferiority hypothesis:

- The NRS score which ranges from 0 to 10 is assumed to be approximately normally distributed.
- The NRS score is to be assessed at 24 weeks (6 months) after the procedure.
- The NRS at 24 weeks (6 months) is expected to be 3.5 in the MENDEC Spine treatment, and 3.5 or more in the Xpede. A difference in NRS score of 1.5 or less is considered clinically unimportant for this comparison. It is considered the maximum acceptable increase in NRS score compared to the MENDEC Spine arm.
- The standard deviation of the NRS score is expected to be approximately 3.27 for each treatment. Common standard deviation will be assumed for both arms.
- The sample size should be sufficient to produce an 80% chance (power) of a significant result at a one-sided 0.025 significance level.

The non-inferiority hypothesis on the NRS requires 152 subjects and including 15% of potential loss-to-follow-up, the total sample size for the study will be 179 randomized subjects by 1:1 randomization schedule. Since there are strata, the sample size should be 180 to be divisible of 18 strata, i.e. 90 patients per arm. If we use $3 * 3 * 2$ strata, the sample size should be 180 to be divisible of 18. Considering an average of 1.35 level per patient (FREE trial 72% with 1 level, 21% with 2 levels, 7% with 3 levels²), we should have around 243 levels treated in 180 patients.

6.2. Primary Endpoint on Vertebral Body Angles

The following assumptions were used for the determination of the sample size for VBA non-inferiority hypothesis:

- The Angulation is assumed to be approximately normally distributed.
- The Angulation is to be assessed at 24 weeks (6 months) after the procedure.
- The Angulation at 24 weeks (6 months) is expected to be 1.2 in the MENDEC Spine treatment, and 1.2 or more in the XPEDE. A difference in Angulation of 2.5 or less is considered clinically unimportant for this comparison (half standard deviation rule). It is considered the maximum acceptable increase in Angulation compared to the MENDEC Spine arm. Standard deviation of 5.0 at 1 month from CAFÉ study was conservatively used to derive the non-inferiority margin of 2.5.
- The standard deviation of the Angulation is expected to be approximately 5.6 for both arms. Standard deviation of 5.6 at 12 months from CAFÉ study³ was conservatively used as the standard deviation for both arms.
- The sample size should be sufficient to produce an 80% chance (power) of a significant result at a one-sided 0.025 significance level.

The non-inferiority hypothesis on the Vertebral Body Augmentation assuming 20% of potential loss-to-follow-up, the total sample size for the study will be 148 randomized subjects by 1:1 randomization schedule. Since there are strata, the sample size should be 162 to be divisible of 18 strata, i.e. 81 patients per arm.

Since final sample size was determined to be 180 patients, i.e. 90 patients per arm.

7. Statistical Methods

7.1. Study Subjects

7.1.1. Disposition of Subjects

Disposition of subjects will be reported following the CONSORT flow Diagram¹. Number of individuals at each stage of study (number of total assessed for eligibility, number enrolled, number analyzed and number with 1 Day post-operative follow-up, 3 months post-operative follow-up and 6 months post-operative follow-up) will be reported by randomization group. Reason for not participation at each stage will be reported where known.

Table 1.2 - Eligibility by Inclusion/Exclusion Criteria - All assessed for eligibility Subjects

Table 1.1 - Summary of Disposition - All Subjects

Figure 1.1.2 - Subject Enrollment Accrual by Site Overtime

Figure 1.1.1 - Flow diagram of Patient Disposition

Xpede Clinical Study

Statistical Analysis Plan

Version 1.0

Page 9 of 19

Medtronic

[figure not shown]

Figure 1.1.1 - Flow diagram of Patient Disposition

7.1.2. Clinical Investigation Plan (CIP) Deviations

All deviations will be collected in the case report form, with the type of the deviation and the reason for the deviation. All Deviations will be reviewed and classified by the clinical study team. Protocol deviation will be defined as major protocol deviation if the deviation impacts the primary objective, for example:

- Missing 6 months follow-up assessment (see table in section 9. 1 for CIP).
- Randomization procedure not followed
- Study treatment not done
- Study treatment deviation

The following tables will describe study deviations:

Xpede Clinical Study

Statistical Analysis Plan

Version 1.0

Page 10 of 19

Medtronic

Table 3.3.1 - Summary of Protocol Deviation by Category

Table 3.3.2 - Summary of Protocol Deviation by Associated Visit

Listing 1 – Protocol deviations

7.1.3. Analysis Sets

The analysis will be performed according the Intention To Treat (ITT) principle and a Per Protocol Set will be used as deemed appropriate. The following subject sets will be used for the analysis respectively:

The ITT analysis will use the Full Analysis Set (FAS), which includes all patients enrolled in the study, signed the Informed Consent, were randomized and received the study treatment.

- The Per Protocol Set (PPS) includes all patients enrolled in the study that meet the inclusion/exclusion criteria with no major protocol deviation (see section 7.1.2) that could impact the clinic outcomes and have 6 months follow-up visits completed. The PPS will be used as secondary analysis.

For those patients who drop out of the study, the analyses will include all data up to the point of their last data collection.

The table below shows which population should be used for each of the planned analysis.

Population set	Baseline assessment	Primary Endpoint	Secondary Endpoints	Safety
ITT	✓	✓	✓	✓*
PP	✓	✓		

*in case of patients enrolled but not randomized, a listing of all the adverse events occurred will be presented.

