9.10. Assessment of Safety

Timely, accurate, and complete reporting and analysis of safety information is crucial for the protection of subjects, clinicians, and the sponsor. Reporting and analysis of safety data are mandated by regulatory authorities worldwide. Medtronic has established Standard Operating Procedures (SOPs) to ensure compliance with global regulatory safety reporting requirements. Study activities are conducted in accordance with these SOPs.

All adverse events are collected throughout the duration of this study, starting from the time of signing the ICF through study closure. Adverse Events are to be reported upon site awareness using an adverse event CRF, capturing date of the event; date site became aware of the event, diagnosis of the event, actions taken, assessment of seriousness, relatedness and outcome.

Unavoidable Adverse Events (refer to Table 7) need not be reported unless the adverse event worsens or is present outside the stated timeframe.

Adverse Events will be recorded and reported according to local regulatory requirements and are outlined in Table 8. It is the responsibility of the Investigator to abide by the adverse event reporting requirements stipulated by local law and the sites' Ethics Committee.

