9.13. Subject Withdrawal or Discontinuation

Every attempt should be made to follow all treated subjects through study closure.

Upon exiting from the study, no further study data will be collected or study visits will occur for the subject. No study specific medical care will be provided for subjects after the study has been completed and subject will be treated according to the standard routine practice after the study period.

All data available through the time of the subject's exit will be used for analysis. In the event of study exit, the investigator should discuss with the subject the plans for future care and treatment. The investigator should explain that the subject will continue to receive standard medical care. Alternative treatment, such as medication options, or follow-up through standard of care procedures instead of study procedures, and medical consequences should also be discussed. The investigator must notify the subject of any significant new findings that may become available during the course of the study, which are pertinent to the safety and well-being of the subject.

Exit

Subjects may be exited from the study for any of the following situations:

- Subject does not meet inclusion/exclusion criteria and has not been treated
- No BKP or VP attempted
- Procedure attempted but no bone cement was injected
- Subject chooses to withdraw from the study
- Investigator deems withdrawal necessary (medically justified or inclusion/exclusion criteria not met, failure of subject to maintain adequate study compliance)

In the event that a subject is exited from the study prior to study closure, all efforts should be made to continue following the subject until all unresolved procedure or product related adverse events are resolved or they are ongoing and no further actions will be taken.

Lost to Follow-up

In the case that the subject is determined to be lost to follow-up, details of a minimum of three attempts and the method of attempt (e.g., one letter and two phone records or two letters and one phone record) to contact the subject must be recorded. In addition, the requirements set by the governing EC/IRB for subjects lost to follow-up must be followed.

10. Risks and Benefits

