7.10. Safety Evaluation

All adverse events are collected throughout the duration of this study, starting from the time of signing the Informe Consent through study closure. Adverse Events will be recorded and reported according to local regulatory requirements. The current version of MedDRA coding will be used.

The following summary tables and supporting data listings:

Table 3.1.2 – Adverse Events by System Organ Class and Preferred Term – FAS

Table 3.1.3 – Adverse Events by System Organ Class, Preferred Term and Relationship to Bone Cement – FAS

Listing 2- Adverse Event – FAS

Listing 3- Adverse Event leading to death – FAS

Xpede Clinical Study

Statistical Analysis Plan

Version 1.0

Page 14 of 19

Medtronic

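### Adverse events in patients randomised but given no cement appear in no safety output named in the SAP, and no rule says how to group patients who received the other cement

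*SAP*

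**What the plan says.** SAP 7.1.3 opens with the principle: "The analysis will be performed according the Intention To Treat (ITT) principle". It then defines the FAS as the set "which includes all patients enrolled in the study, signed the Informed Consent, were randomized and received the study treatment". In the population table of that section, the Safety column is ticked only in the ITT row. No separate safety or as-treated set is defined. A footnote to that tick adds the one exception: "in case of patients enrolled but not randomized, a listing of all the adverse events occurred will be presented".

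SAP 7.10 names four adverse event outputs. The first is "Table 3.1.2 – Adverse Events by System Organ Class and Preferred Term – FAS". The others are a second table that adds the judged relationship to the cement (3.1.3), a listing of all events (Listing 2) and a listing of those that led to death (Listing 3). All three carry the FAS label too.

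On collection, Protocol 9.10 says: "All adverse events are collected throughout the duration of this study, starting from the time of signing the ICF through study closure". Protocol 9.3 places randomisation after consent and before surgery. It also limits endpoint analysis to randomised patients who received treatment, and adverse events are a secondary endpoint (Protocol 5.2.2). Protocol 9.13 lists among the exit reasons that no procedure was attempted, and also "Procedure attempted but no bone cement was injected". SAP 7.1.2 gives treatment not done and treatment deviation as examples of major deviations. Protocol 13.4 removes patients given the wrong treatment from the per-protocol set and says nothing about how their adverse events are grouped.

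**The concern.** The footnote in SAP 7.1.3 shows that the authors meant to account for adverse events outside the FAS. It covers patients who were never randomised but misses those who were randomised and then not treated. An event in that second group, for example at anaesthesia or access in an abandoned procedure, would be in the database. A programmer following the SAP would nevertheless have no table or listing to put it in. The same holds for a death, because Listing 3 is also on the FAS.

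Grouping raises a second question. Table 3.1.3 reports relationship to bone cement. If a patient is given the other product, the reader needs to know which column holds the events, and the SAP does not say.

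This is a pre-market registration trial whose stated purpose (Protocol Synopsis) covers non-inferiority in safety as well as efficacy. Its final report should account for every collected adverse event and show the product to which the patient was exposed.

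**Working it through.** The main check is textual: take each kind of patient and see which named output carries the adverse events.

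| Patient | In the FAS? | Tables 3.1.2–3.1.3, Listings 2–3 | Footnote listing |
|---|---|---|---|
| Randomised, cement injected | Yes | Yes | No |
| Enrolled, not randomised | No | No | Yes |
| Randomised, no procedure attempted | No | No | No |
| Randomised, procedure attempted, no cement injected | No, if study treatment means the cement | No | No |
| Randomised, other cement injected | Not stated | Grouping not stated | No |

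Rows 3 and 4 are the gap. Study treatment is not formally defined. If it meant the procedure rather than the cement, row 4 might count as treated, but row 3 would still be omitted.

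Other named outputs do not fill the gap:

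- Disposition (SAP 7.1.1) counts patients, and the deviation tables and Listing 1 (SAP 7.1.2) record deviations. Neither reports adverse events.
- The by-centre display of safety events (SAP 7.3) names no population, but SAP 7.1.3 puts safety on the ITT row.
- The time-to-event analyses in Protocol 13.4 count exposure from the index procedure, so a patient with no procedure has no starting point.

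**Size of the omission.** The base is the planned total in SAP 6.1: 152 / (1 − 0.15) = 178.8, so 179, rounded to 180 (90 per arm). The documents give no proportion randomised but untreated, so 1–5% is assumed:

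- 1%: 0.01 × 180 = 1.8, about 2 patients
- 2%: 0.02 × 180 = 3.6, about 4 patients
- 5%: 0.05 × 180 = 9 patients

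With an assumed 10% chance that such a patient has an adverse event, the chance of at least one patient with an omitted event is 1 − 0.9^k:

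- k = 2: 1 − 0.81 = 0.19
- k = 4: 1 − 0.656 = 0.34
- k = 9: 1 − 0.387 = 0.61

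**Size of misattribution, if events were grouped by assigned cement.** Suppose a fraction c of each arm receives the other product and risk follows the product received. The observed difference is then (1 − 2c) × the true difference. For an assumed true difference of 10 percentage points:

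- c = 1%: 0.98 × 10 = 9.8 points
- c = 5%: 0.90 × 10 = 9.0 points

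The effect is small, but it pulls the two products together.

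**The case against.** The strongest case against has five parts.

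1. **Serious events are not hidden.** Protocol Table 8 sends them to the authorities and ethics committee within 24 hours. The sponsor reports serious events, and device deficiencies with serious potential, within 5 working days. None of this depends on the FAS. Protocol 9.13 also asks that unresolved procedure- or product-related events be followed after exit. This stands: a reader might infer that events would be lost to regulators, and the documents do not support that. The gap is confined to the planned tables and listings.

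2. **No sentence prescribes grouping by assigned cement.** This also stands. A reader might infer from the ITT label that the SAP attributes safety to the assigned rather than the received product, but the SAP is silent. The silence is what needs correcting.

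3. **Tables on treated patients are a legitimate choice.** Protocol 9.3 and 13.4 require treatment for endpoint analysis and for the FAS. Moving uninjected patients into the adverse event tables would conflict with Protocol 9.3. This stands and shapes the fix: the tables stay as they are and the listing is widened.

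4. **Cement that sets before delivery is not a good example.** Without harm to the patient it is a device deficiency under Protocol Table 6, recorded separately from adverse events. This stands, and the point does not rely on that case.

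5. **The mock tables are in a separate document (SAP 10.1).** They may contain an output not named here, so the conclusion is limited to outputs named in the protocol and SAP.

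None of these supplies a place for the adverse events of a randomised, untreated patient.

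**Conclusion.** The gap is real and follows from the SAP's own labels: every adverse event table and listing it names is on treated patients, and the one exception stops at patients who were not randomised. The grouping rule for patients given the other cement is missing. Attribution by assigned product is the likely default under the ITT heading, but it is an inference.

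The expected size is modest. The figure of 2 to 9 patients rests wholly on the assumed 1–5%, and the 19–61% chance of an omitted event also rests on the assumed 10% risk. Baseline and procedure may fall on the same day (Protocol Table 5), which can shorten the time in which a randomised patient goes untreated. The case for acting is that the omission is clear and the correction nearly free, not that a large bias is expected.

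**What to change.** Make two changes to the SAP.

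1. In the footnote to SAP 7.1.3, replace the restriction to non-randomised patients. The adverse event listing, including events leading to death, should cover every consented patient outside the FAS, whether or not randomised, and show the assigned arm (if any) and whether a procedure was started. Refer to consent rather than enrolment, because Protocol 8.2 makes enrolment depend on eligibility as well as consent. Defined this way, the listing is complete whichever meaning of study treatment applies.

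2. In SAP 7.10, state that Tables 3.1.2 and 3.1.3 and Listings 2 and 3 group treated patients by the cement actually received, with a note identifying any patient whose received and assigned cement differ.

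The tables stay on treated patients, consistent with Protocol 9.3 and 13.4, so on this reading no protocol change is needed. The cost is SAP wording and a population flag. Adverse events are already collected from consent, and the procedure record (Protocol 9.6) already covers the cement used.
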